Duration of treatment with avelumab	Treatment pattern from avelumab initiation	Between avelumab initiation and end of follow-up	Will be derived based on the date of avelumab initiation (index date) and the last date of avelumab treatment. The last day of avelumab treatment will be calculated based on the last recorded date of avelumab treatment received + 14 days. A gap of 30 consecutive days of no treatment with avelumab will be used to establish the last recorded date of avelumab treatment received.

Variable	Role	Time of measurement	Operational definition
Time interval between start of avelumab and start of 2L therapy	Treatment pattern from avelumab initiation	Between avelumab initiation and end of follow-up	Time interval will be derived using the dates of avelumab initiation and initiation of first regimen of 2L therapy. This parameter will be calculated only among patients who go on to receive 2L therapy after avelumab initiation

Number of patients who receive 2L therapy	Treatment pattern from avelumab initiation	Between avelumab initiation and end of follow-up	Number of patients who received 2L therapy after initiating avelumab
Number of patients who discontinue avelumab and start 2L therapy	Treatment pattern from avelumab initiation	Between avelumab initiation and end of follow-up	Number of patients who discontinue avelumab and subsequently receive 2L therapy
SACT regimen received as 2L therapy	Treatment pattern from avelumab initiation	Between avelumab initiation and end of follow-up	Among the number of patients receiving 2L therapy, unique SACT regimen reported as 2L therapy after avelumab initiation any time during follow-up
Number of SACT cycles received as 2L therapy	Treatment pattern from avelumab initiation	Between avelumab initiation and end of follow-up	Number of cycles received as 2L therapy after avelumab initiation
rwTTD from initiation of avelumab	Treatment pattern from avelumab initiation	Between avelumab initiation and end of follow-up	
Time between avelumab initiation until the earliest of:
 
 • Date of discontinuation (a gap of 30 days without treatment with avelumab will be used to establish a patient as having discontinued avelumab) • Having a subsequent systemic therapy regimen • Date of death from any cause 
See Table 1 for other censoring points

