*In June 2020, the FDA approved avelumab for maintenance treatment in patients with locally advanced or metastatic UC that have not progressed with 1L platinum-containing chemotherapy (9). In January 2021, the European Commission (EC) approved avelumab as a monotherapy for the 1L maintenance treatment of adult patients with locally advanced or metastatic UC who are progression-free following platinum-based chemotherapy (10). Avelumab is a human monoclonal Immunoglobulin G1 (IgG1) antibody that targets the immunomodulatory cell surface ligand protein, PD-L1. The JB100 trial was designed to be a randomized, multicentre and open label study conducted to understand the efficacy of maintenance avelumab. Maintenance therapy with avelumab in addition to BSC showed improved overall survival compared to BSC alone in patients with advanced UC whose cancer had not progressed following 1L*

PFIZER CONFIDENTIAL

CT24-WI-GL03-RF03 0.2 *Non-Interventional Statistical Analysis Plan For Secondary Data Collection*  
*Study 01-Jun-2020*  
*Page 10 of 34*

*platinum-based chemotherapy (11,12). Overall survival at 1 year was 71% in the avelumab group and 58% in the control group, with a hazard ratio for death reported at 0.69 (95% confidence interval, CI, 0.56 – 0.86,  $p=0.001$ ). Median overall survival was 21.4 months in the avelumab group vs. 14.3 months in the control group and median progression-free survival was 3.7 months vs. 2.0 months, respectively. Patients received avelumab following a treatment-free interval of four to ten weeks after receipt of four to six cycles of chemotherapy with gemcitabine plus cisplatin or carboplatin. AEs of any grade occurred in 98.0% of patients in the avelumab group and 77.7% in the control group (13).*

*This NIS aims to understand clinical outcomes of patients treated with avelumab as monotherapy for the 1L maintenance treatment of locally advanced or metastatic UC who are progression-free following platinum-based chemotherapy, in a real-world setting in the UK.*

PFIZER CONFIDENTIAL

CT24-WI-GL03-RF03 0.2 *Non-Interventional Statistical Analysis Plan For Secondary Data Collection*  
*Study 01-Jun-2020*  
*Page 11 of 34*

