### 5.2 SECONDARY OBJECTIVES:

1. To describe the clinical and demographic characteristics of the study population at first diagnosis of UC, diagnosis of locally advanced or metastatic disease and at avelumab treatment initiation.
2. To describe real-world progression-free survival (rwPFS) in the study population
3. To describe treatment characteristics of 1L anti-cancer therapies received prior to the initiation of avelumab as 1L maintenance therapy in the study population
4. To describe treatment patterns after initiation of avelumab as 1L maintenance therapy in the study population
5. To describe the AEs explicitly attributed to avelumab in the study population
6. To describe real-world all-cause healthcare resource burden associated with avelumab therapy in the study population

PFIZER CONFIDENTIAL

CT24-WI-GL03-RF03 0.2 *Non-Interventional Statistical Analysis Plan For Secondary Data Collection*  
*Study 01-Jun-2020*  
Page 12 of 34

[figure not shown]

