### **Follow-up and Censoring**

The follow-up period for participants will be from the index date to the earliest date of:

- Death (as recorded in eCRF Q35)
- Loss to follow up (as recorded in eCRF Q36)
- 24 months after the index date

For each participant, the censoring date used for the time-to-event analyses will be the earliest date of loss to follow up or 24 months after the index date, as recorded on the eCRF. Note that death is treated as an event in the time-to-event analyses, therefore not used as a censor point. For the time-to-progression variable only, the start date of 2L SACT will be used as an additional censoring point. Specific definitions of events and

PFIZER CONFIDENTIAL

CT24-WI-GL03-RF03 0.2 *Non-Interventional Statistical Analysis Plan For Secondary Data Collection*  
*Study 01-Jun-2020*  
Page 15 of 34

censoring for each time-to-event variable individually are provided in the relevant section of the table in [Section 8](#).

For a subset of the variables, data will be collected from medical records prior to the index date and recorded retrospectively in the eCRF. This look-back period will cover the period for each patient from the date (inclusive) of their first UC diagnosis (relating to diagnosis at any stage; as recorded on the eCRF Q5) to the day before the index date (inclusive). This look-back period applies to some clinical and demographic characteristics to be described for Objective 2, as well as some pre-avelumab treatment patterns to be analysed for Objective 4 (see [Section 8](#) for full details of each variable and the time period to be used for data collection).

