Adverse events	Patient outcome	From index date to date of censoring	The number of separate AEs recorded per patient (with explicit linkage in the medical notes to avelumab) will be calculated using data from eCRF Q39 (each reported event on the eCRF counts as a separate AE). This will be used to calculate the rate of events per patient per year of follow-up time
Objective 7: to describe healthcare resource burden associated with avelumab (table shell Table 2.6)			

PFIZER CONFIDENTIAL

CT24-WI-GL03-RF03 0.2 *Non-Interventional Statistical Analysis Plan For Secondary Data Collection*  
*Study 01-Jun-2020*  
 Page 26 of 34

Accident and Emergency visits	Healthcare resource burden indicator variable	From index date to date of censoring	The number of accident and emergency visits recorded per patient (each reported visit on the eCRF Q37 counts as a separate visit) will be used to calculate the rate of events per patient per year of follow-up time
Hospitalisations	Healthcare resource burden indicator variable	From index date to date of censoring	The number of hospital admissions recorded per patient (each reported visit on the eCRF Q38 counts as a separate visit) will be used to calculate the rate of events per patient per year of follow-up time
Duration of hospitalisation	Healthcare resource burden indicator variable	From index date to date of censoring	The total number of days duration of hospitalisation recorded per patient will be calculated as the sum of the duration of all separate hospitalisations reported per patient in eCRF Q38 (where the duration of each event is the number of days between the reported start and end date, inclusive of the start and end dates). This will then be used to calculate the number of days of hospitalisation per patient per year of follow-up time

PFIZER CONFIDENTIAL

CT24-WI-GL03-RF03 0.2 *Non-Interventional Statistical Analysis Plan For Secondary Data Collection*  
*Study 01-Jun-2020*  
 Page 27 of 34

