#### Analysis of continuous variables

All continuous variables will be described using the following statistics: number of observations, mean, standard deviation, median, minimum, and maximum values, first and third quartile (Q1 and Q3). The mean, median, Q1 and Q3 will be displayed to one decimal place. The standard deviation will be displayed to two decimal places.

The number of AEs, number of hospitalisations, duration of hospitalisation, and number of Accident & Emergency visits will each be used to calculate a rate per patient per year of follow-up time. This will be calculated as the total number of incident events (or total number of days hospitalisation) recorded per patient during the follow-up time divided by the total follow-up time (time at risk) per patient in years. All rate variables will be presented in the same way as for the other continuous variables.

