### **Further limitations**

All analyses are carried out on the FAS which includes all patients irrespective of the duration of avelumab treatment. As such, duration of avelumab treatment could confound the interpretation of some results, especially the efficacy endpoints (rwOS and rwPFS) and AEs, by inclusion of patients who may have started avelumab therapy but discontinued treatment after a short period. To account for this, the results will include descriptive statistics of treatment duration in the study population.

Research Objective 6 includes the descriptive analysis of AEs which are explicitly attributed to avelumab treatment, based on AEs being directly linked to avelumab in medical notes. Given that the data for analysis will be extracted from the standard medical records via eCRF and largely based on retrospective assessment of participants, it is unlikely that explicit linkage between AEs and avelumab will be consistently recorded. This means that descriptive statistics of AEs are likely to underestimate the numbers of AEs that are attributed to avelumab in a real-world setting.

The follow-up period for this study has been defined as 24 months from the date of avelumab treatment initiation, based on previous clinical trial data that median overall survival for patients receiving avelumab as 1L maintenance therapy in locally advanced or metastatic UC is 21.4 months (13). However, it is possible that this focus on a relatively short follow-up period will overlook longer-term outcomes (including, but not limited to, efficacy endpoints and safety events).

PFIZER CONFIDENTIAL

CT24-WI-GL03-RF03 0.2 *Non-Interventional Statistical Analysis Plan For Secondary Data Collection*  
*Study 01-Jun-2020*  
Page 31 of 34

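### Avelumab-attributed adverse event rates are divided by all follow-up rather than time on avelumab, so the reported rate depends on how long patients live after stopping

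*SAP*

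**What the plan says.** SAP 10.3 (Analysis of continuous variables) turns four counts into per-patient rates: AEs, hospitalisations, hospital days, and accident and emergency visits. Each patient's total is "divided by the total follow-up time (time at risk) per patient in years". These rates are then summarised like any other continuous variable (mean, median, quartiles). SAP 8, Objective 6, restricts the AE count to events that the medical notes link to avelumab and adds: "This will be used to calculate the rate of events per patient per year of follow-up time".

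SAP 6.2 (Follow-up and Censoring) fixes the denominator: "The follow-up period for participants will be from the index date to the earliest date of" death, loss to follow-up, or "24 months after the index date". Stopping avelumab does not end it. Starting second-line therapy is an extra censoring point for time to progression only.

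SAP 10.5 (Further limitations) accepts that treatment duration could confound the AE results and answers: "To account for this, the results will include descriptive statistics of treatment duration in the study population". For resource use, SAP 5.2 states the aim as "To describe real-world all-cause healthcare resource burden associated with avelumab therapy in the study population".

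**The concern.** The numerator is limited to events caused by the drug, in the judgement of the treating team, while the denominator includes time after the drug has stopped. Calling all of that time at risk is hard to defend for avelumab-attributed events.

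Take two patients with the same experience on treatment, each with 2 attributed AEs in 3 months on avelumab:

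- On-treatment rate for both: 2 / (3/12) = 8 per year.
- One dies at month 4: reported rate 2 / (4/12) = 6 per year.
- The other is alive at month 24: reported rate 2 / (24/12) = 1 per year.

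The six-fold gap reflects survival after stopping, not toxicity. A reader who takes the figure as a safety rate for avelumab would think the drug better tolerated than it was. The same section of the SAP already expects AEs to be under-counted because attribution is recorded inconsistently, and this dilution adds to that.

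For resource use, all-cause admissions and visits continue through second-line therapy and up to death. An output headed as burden associated with avelumab therapy could be read as burden arising while on avelumab.

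**Working it through.** **The plan's own figures.** The documents give no AE rate, resource rate or time on treatment to reproduce. The survival inputs in protocol 9.4 do reproduce. With 100 patients, deaths are 100 × (1 − 0.713) = 28.7 by 12 months (stated 29) and 100 × (1 − 0.48) = 52 by 24 months (stated >50). Clopper-Pearson intervals are 61.1–79.6% and 37.9–58.2%, matching Table 5.

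**Mean follow-up.** Use a piecewise-exponential survival curve through 71.3% at 12 months and 48% at 24 months, with no loss to follow-up. The monthly hazards are −ln(0.713)/12 = 0.02819 and −ln(0.48/0.713)/12 = 0.03297. The area to 24 months is (1 − 0.713)/0.02819 + (0.713 − 0.48)/0.03297 = 10.18 + 7.07 = 17.25 months. Adding the trial median of 21.4 months as a third point gives 17.1.

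**Mean time on avelumab (assumed).** The only nearby figure is from JAVELIN Bladder 100: "median progression-free survival was 3.7 months vs. 2.0 months, respectively". I take 3.7 months as the low end and 6 and 9 months as alternatives. Stopping or death is treated as one exponential event with median m, so death is counted once, as in the SAP's definition of time to discontinuation. With λ = ln 2 / m, mean time on avelumab = (1 − e^(−24λ))/λ.

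| Median m (months) | Mean on avelumab (months) | Share of 17.25 | Pooled understatement |
|---|---|---|---|
| 3.7 | 5.28 | 31% | 3.3-fold |
| 6 | 8.12 | 47% | 2.1-fold |
| 9 | 10.94 | 63% | 1.6-fold |

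The pooled understatement is 17.25 divided by mean time on avelumab, if attributed AEs occur only on treatment.

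**The statistic the SAP plans.** The SAP summarises per-patient rates, so the relevant factor is 1 / mean(time on avelumab ÷ follow-up). I simulated stopping independent of survival, scaled so that stopping or death has median m, with a true rate of 3 per on-treatment year.

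| Median m (months) | Mean of per-patient rates | Understatement | Pooled rate | Understatement |
|---|---|---|---|---|
| 3.7 | 1.20 | 2.5-fold | 0.92 | 3.3-fold |
| 6 | 1.65 | 1.8-fold | 1.41 | 2.1-fold |
| 9 | 2.08 | 1.4-fold | 1.89 | 1.6-fold |

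**Sensitivity.** If the first to stop are also the first to die (ranks fully linked), the per-patient factors become 3.8, 2.5 and 1.8, and the pooled factors stay at 3.3, 2.1 and 1.6. A long-tailed discontinuation curve (Weibull shape 0.6) with median 3.7 months gives a pooled factor of 2.3, and with median 10 months 1.4.

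**When is more than half of follow-up off avelumab?** Only if the median is below about 6.4 months (exponential) or 4.8 months (long-tailed), using mean follow-up of 17.1 months.

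**The case against.** Several points on the other side are sound.

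- **Treatment duration is unknown.** A reader might infer that most follow-up is off avelumab. The documents do not show this. Progression is not itself a discontinuation event in protocol Table 3 or SAP 8, so median progression-free survival is only a proxy, and at a 9-month median about 63% of follow-up is on treatment.
- **The dilution is uneven.** It is nil for patients who die or reach 24 months still on avelumab, and it differs between per-patient and pooled summaries.
- **Resource use follows the protocol.** A reader might infer that the Objective 7 rates are miscalculated. Protocol Table 4 sets the window from initiation to end of follow-up. Protocol 9.6.3 explains that reasons for admission are hard to extract, so only all-cause hospitalisation is analysed. Second-line and end-of-life care are therefore included by design. What remains is a labelling point.
- **The dates may not all exist.** A reader might assume that every date needed is already collected. SAP 8 shows event start and end dates only for hospital stays (Q38), not for AEs (Q39) or emergency visits (Q37), and the form is not supplied.
- **On-treatment rates per patient are unstable.** One AE after one dose, over a 14-day window, is 1 / (14/365.25) ≈ 26 per year.
- **The issue is partly disclosed.** The rate is described as per year of follow-up, and SAP 10.5 admits confounding by duration. The share of patients with any AE and the time to discontinuation are also reported. The study is descriptive, and overall survival is unaffected.

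These points limit the size of the finding and shape the remedy. They do not remove the mismatch between a drug-attributed numerator and a denominator that runs on after the drug. A separate duration summary cannot re-base per-patient rates.

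**Conclusion.** The point holds for the attributed-AE rate. As planned, it is not a rate per time exposed to avelumab, and it varies with survival after stopping. For assumed medians of 3.7 to 9 months to stopping or death, the planned mean of per-patient rates would be about 2.5- to 1.4-fold below the on-treatment rate, and a pooled rate 3.3- to 1.6-fold below. This rests on attributed AEs arising mainly on treatment, the trial survival figures in protocol 9.4, no loss to follow-up, exponential stopping with death counted once, and stopping independent of survival. Late-onset attributed AEs would shrink the gap. Linking stopping to survival would widen the per-patient one. The direction does not require that most follow-up be off avelumab; the size depends on the unknown treatment duration. The share of patients with any AE is not affected. For Objective 7 the finding is limited to labelling, with an optional split.

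**What to change.** In SAP 8 (Objective 6) and SAP 10.3:

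1. Add a pooled exposure-based rate: total attributed AEs with onset on treatment, divided by total on-avelumab time. Run that time from Q25 to the last avelumab date plus the 14 days in protocol Table 3 ("last recorded date of avelumab treatment received + 14 days"), ending no later than the end of follow-up. Use the same window for numerator and denominator. Those 14 days were written to define treatment duration, not a safety window, so the SAP should state that it is adopting them for this purpose.
2. Report attributed AEs with later onset as separate counts, so that none are lost.
3. Keep the existing rate, labelled *per year of follow-up*, and delete the time-at-risk description.
4. Reconcile the two duration definitions. Protocol Table 3 adds 14 days and uses a 30-day gap; SAP 8 adds no days and disregards pauses.
5. Confirm that Q39 records onset dates. If it does not, the on-treatment numerator cannot be built.

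For Objective 7, keep the protocol's all-cause window but label it *from avelumab initiation to end of follow-up*. Where event dates allow, add one split of events and person-time at avelumab discontinuation (Q27). With about 100 patients, a finer split would leave sparse cells.

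The cost is SAP wording and a few table rows, plus the check on Q39 and Q37 dates. The drawback is that delayed immune-related events fall outside the on-treatment rate, which is why the separate count is needed.

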### **Analysis of categorical variables**

Categorical variables will be described using frequency counts and percentages. Calculation of percentages will include a category for missing values where applicable for a given variable, therefore counts of missing observations will be included in the denominator and presented as a separate category. All percentages will be reported to one decimal place.

## **10.4 QUALITY CONTROL**

All aspects of study design and management, from protocol to ongoing site management, will be conducted within the framework of the IQVIA Quality Management System (QMS) and in accordance to IQVIA and/or Pfizer's Standard Operating Procedures.

## **10.5 STUDY LIMITATIONS**

### **Selection bias**

Selection bias could be introduced to the study via patient selection methods, since the study population is small and only includes participants from EAMS and EAMS extension NHS sites, which could differ demographically from NHS sites more generally. These patient selection methods are necessary to find sufficient numbers of patients using avelumab therapy. Given that the date for the EMA license for avelumab is 30th June 2020, low numbers of patients are expected to be using it, therefore the sample size for this study is limited to the first 100 eligible patients.

### **Information bias**

Most participants will be assessed retrospectively, although a minority will be identified after the study has started (ie, assessed prospectively). The data for the patients who are prospectively assessed is expected to be of a higher quality in comparison to the data for patients who are retrospectively assessed, although this will depend on the accuracy of the medical records.

The proposed data source to be used is eCRF, and so not all variables are expected to be recorded consistently in the available electronic medical records and charts, especially for patients who are assessed retrospectively. However, the primary endpoint (rwOS) is expected to be well-recorded in hospital system. This potential limitation will be

PFIZER CONFIDENTIAL

CT24-WI-GL03-RF03 0.2 *Non-Interventional Statistical Analysis Plan For Secondary Data Collection*  
Study 01-Jun-2020  
Page 30 of 34

particularly important for variables which involve, for example, computing time windows or complex definitions of staging, at the point of eCRF data collection. This risk will be minimised by providing hospital staff with appropriate information and training in the information packs provided with the study materials. Site monitoring, and where required, source data verification (SDV) will also be carried out to aim to reduce and minimise the risk of missing data or data errors.

